1 INTRODUCTION

1.1 Study Purpose

Medtronic, Inc. is sponsoring a quality improvement study called the “Registry to Improve the Adoption of Consensus Treatment Guidelines” (IMPROVE Brady). It is hypothesized that the use of a practice-specific process improvement intervention consisting of education, diagnostic algorithm(s) and documentation tools that advocate and reinforce adherence to consensus treatment guidelines will improve the quality of care for patients with sinus node dysfunction (SND).

The study is expected to provide evidence to support claim(s) that:

- Education and process improvement initiatives can improve the diagnosis of and appropriate therapy application for SND
- The quality improvement methods studied have general applicability and can be used by all centers
- Appropriate treatment minimizes caregiver burden
- Appropriate treatment improves quality of life (QOL) and functional status compared to pre-implant

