4.3 Study Design

There are two phases to IMPROVE Brady:

Phase I: This phase of the study serves as a control period. During Phase I physicians will assess and treat subjects per their site's standard care practice. Enrollment for Phase I is anticipated to occur for approximately 12 months but will continue until 550 subjects have been enrolled for the geography/country. For subjects enrolled during Phase I, collection of diagnostic assessment and implant data will be complete 6 months after the last enrollment for the geography/country. At that time, all Phase I subjects will be exited.

If a center becomes active after the geography/country enrollment goal for Phase I has been met or the center did not enroll at least 10 subjects before Phase I enrollment stopped then the center will enroll Phase I subjects until 10 subjects have been enrolled at that center. Once 10 subjects have been enrolled at the center, enrollment will stop and the subjects will be followed for a maximum of 6 months and exited from the study.

Phase II:

The objective of the IMPROVE Brady study is to provide investigators with comprehensive resources that may be adapted by the Principal Investigator and his/her colleagues to create a practice specific process improvement intervention to improve the quality of care for patients.

At the completion of Phase I, the Principal Investigator and co-investigators will complete an educational workshop and be given access to the IMPROVE Brady toolkit. In addition, the Principal Investigator and his/her colleagues are encouraged to adapt tools from the IMPROVE Brady toolkit to create a practice specific process improvement intervention.

Immediately following completion of the educational workshop, study investigators will receive written authorization from Medtronic that they are authorized to enroll subjects in Phase II. Enrollment during this phase is anticipated to occur for approximately 18 months per geography/country.

[figure not shown]
The IMPROVE Brady process improvement intervention toolkit may include an education workshop, diagnostic algorithm(s), patient video and tools for investigators to educate their patients on their disease state, available therapy options, and benefits and risks associated with the therapy options.

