At the completion of Phase I, the Principal Investigator and co-investigators will complete an educational workshop and provided access to the IMPROVE Brady toolkit. The Principal Investigator and his/her colleagues are encouraged to use the toolkit to create a practice specific process improvement intervention regarding the diagnosis and treatment plan for patients. The educational workshop and toolkit is the intervention being examined, in the study. The IMPROVE Brady toolkit may include, but not limited to, diagnostic algorithm(s), patient video and tools for investigators to educate their patients about their disease state, available therapy options, and benefits and risks associated with the therapy options. Information collected in Phase II will be identical to Phase I regarding what was done to diagnose a patient and, if applicable, information regarding the device that was implanted.

CLINICAL STUDY OBJECTIVES

Primary objectives

1. Evaluate the impact of the intervention on the diagnosis of SND
2. Evaluate the impact of the intervention on SND subjects that receive an indicated IPG device

Secondary objectives

1. The key secondary objectives with pre-specified hypotheses to be tested include:
2. Describe the diagnosis and treatment of Phase I subjects

3. Evaluate the change in time to diagnosis of SND before and after intervention
4. Evaluate the change in the time to receiving an indicated IPG device for SND subjects before and after intervention
5. Evaluate the caregiver burden between pre-implant and 6 months post-implant
6. Evaluate change in Quality of Life (QOL) and functional status between pre-implant
7. and 6 months post-implant

Main Inclusion / exclusion criteria (not an exhaustive list)

Inclusion Criteria:

- Patient is at least 18 years of age
- Patient's heart rate meets at least **one** of the following:
 - Patient has a sinus rate \leq 50 **OR** a junctional escape rhythm no faster than 50
 - Patient has a history of exercise intolerance
- Patient complains of general fatigue, shortness of breath, shortness of breath with exertion, syncope, light headed dizziness, palpitations, lethargy, dyspnea **OR** malaise within the last 30 days that are not related to other discovered causes (such as untreated hypothyroidism or anemia).

Exclusion Criteria:

- Patient has type II 2nd degree AV block, High degree AV block (2:1, 3:1, 4:1 etc.) or 3rd degree AV block
- Patient has recent history of blood loss

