4.1. Primary Objective(s) or Main Objective(s)

This study is exploratory in nature and there are no specified hypotheses or performance requirements for the Primary Objectives. All mentions of the intervention in the objectives below refer to the process improvement intervention that will be implemented at the start of Phase II. All mentions of the diagnosis of SND refer to symptomatic SND.

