8.2. General Methodology

8.2.1. Special Considerations

The study will have an enrollment restriction. The maximum number of subjects to be enrolled at any given study center is 20% of the expected sample size in that geography; 20% of 1650 subjects equals 330 subjects per study center.

Sample size calculations will account for an attrition rate in the study of 10%.

An analysis will be built to examine temporal confounding. Since the study design does not randomize the treatment and control subjects it is possible that the time elapsed over Phase I and Phase II of the study will confound the results. To examine the possibility of temporal confounding, an interrupted time series regression analysis will be performed. This analysis will adapt Rubin's causal model for rate parameters.

This document is electronically controlled. Printed copies are considered uncontrolled.

Confidential

Rubin's causal model for linear outcome Y is $Y = \beta_0 + \beta_1 X + \beta_2 D$, where X is time and D is a dummy variable for group assignment, before and after intervention. To adopt this model for rate parameters estimated in the primary objectives of the study, the model to be fit is $\log(Y) = \beta_0 + \beta_1 X + \beta_2 D + \log(Z)$ where Y is a binary response to indicate an SND diagnosis and Z is the amount of subject follow-up. The same model will also be fit to model the rate of IPG treatment. If an association is seen by testing β_1 , then temporal confounding exists.

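### The time model in SAP 8.2.1 has no Phase II slope, so gradual uptake of the intervention can be read as temporal confounding and can pull the estimated step towards or below no effect

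*Protocol*

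**What the plan says.** Protocol section 1.1 states the hypothesis in terms of the "use of a practice-specific process improvement intervention consisting of education, diagnostic algorithm(s) and documentation tools". Section 4.3 gives investigators the workshop and toolkit access at the end of Phase I, and practices are then "encouraged to adapt tools from the IMPROVE Brady toolkit to create a practice specific process improvement intervention". No deadline or completion check is attached to that step. Enrolment in Phase II does not wait for it: "Immediately following completion of the educational workshop, study investigators will receive written authorization from Medtronic" to begin enrolling.

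Appendix F describes the intervention more narrowly: "The educational workshop and toolkit is the intervention being examined". SAP section 4.1 refers to the "process improvement intervention that will be implemented at the start of Phase II", and SAP sections 8.5.1.1 and 8.5.2.1 count all of Phase II as post-intervention.

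SAP section 8.2.1 recognises that the unrandomised sequence may be confounded by time and specifies an interrupted time series. It has a single coefficient β1 for time X, a step β2 for phase D, and follow-up Z as offset. It is fitted to diagnosis and again to IPG treatment. The reading rule is that if testing β1 shows an association, "then temporal confounding exists".

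**The concern.** The model allows two shapes: a trend running through both phases at one rate, and a jump at the start of Phase II. A practice change that builds up over months is neither. It is flat in Phase I and rises within Phase II. Having no term for that rise, the model takes it into the common slope, extrapolates the slope back over Phase I and across the gap, and shrinks the step to compensate.

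Two things follow when there is no secular change and the intervention works. The step estimate is biased towards or below a ratio of 1, whether or not β1 reaches significance. And when β1 is significant, the SAP's own rule gives the wrong explanation. SAP section 6 leaves South Asia as the only geography with both phases, so the before-after contrast and its time check rest on that one data set.

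**Working it through.** **Inputs from the documents.** 500 evaluable subjects in Phase I and 1,000 in Phase II, 20% versus 28% diagnosed at 6 months, type I error 0.05 and power 0.90 (SAP 8.5.1.2). Enrolment of about 12 and 18 months, with 6 months of follow-up after the last Phase I enrolment (Protocol 4.3), taken here as a 6-month gap.

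**Assumptions.** The documents give no adoption lag, so uptake is taken as linear from 20% to 28% over the first L months of Phase II, with L varied. Phase I is flat at 20% and there is no secular trend. Time is enrolment month, exposure is equal, and tests are two-sided at 0.05 with model-based standard errors.

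**Step 1: the plan's own figure.**
- Pooled rate: (100 + 280)/1,500 = 0.2533.
- SE under the null: √(0.2533 × 0.7467 × (1/500 + 1/1,000)) = 0.02382.
- SE under the alternative: √(0.16/500 + 0.2016/1,000) = 0.02284.
- z = (0.08 − 1.96 × 0.02382)/0.02284 = 1.46, so power is 0.93 (0.92 with continuity correction).

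This agrees with the stated 0.90 for an increase of at least 8 points.

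**Step 2: true average effect under gradual uptake.** The Phase II mean is 28% − 8 × L/36 points:
- L = 6: 26.7%, ratio 1.33
- L = 12: 25.3%, ratio 1.27
- L = 18: 24.0%, ratio 1.20

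**Step 3: what the SAP model returns** (1,500 simulated trials per row, 6-month gap).

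| Uptake period | True average ratio | Mean β1 per month | Step ratio exp(β2) | β1 significant |
|---|---|---|---|---|
| 0 months | 1.40 | 0.000 | 1.40 | 2% |
| 3 months | 1.37 | 0.006 | 1.20 | 5% |
| 6 months | 1.33 | 0.0111 | 1.05 | 14% |
| 12 months | 1.27 | 0.0162 | 0.90 | 28% |
| 18 months | 1.20 | 0.0160 | 0.86 | 26% |

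Separate reruns gave step ratios of 1.04 at 6 months and 0.88 at 12, and significance rates of 14%, 23%, 31% and 27% at 6, 9, 12 and 18 months. With no gap, the step ratios at 6, 12 and 18 months are 1.13, 0.99 and 0.95.

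**Step 4: check by hand.** The fit reproduces each phase's total, so exp(β2) is close to the average ratio divided by exp(β1 × distance between phase midpoints). The midpoints are month 6 and month 12 + 6 + 9 = 27, so the distance is 21 months.
- L = 6: 1.333/exp(0.0111 × 21) = 1.333/1.262 = 1.06
- L = 12: 1.267/exp(0.0162 × 21) = 1.267/1.405 = 0.90
- L = 18: 1.20/exp(0.0160 × 21) = 1.20/1.399 = 0.86

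**Step 5: limits of the Phase I slope.** With a Phase II slope added and no secular trend, the Phase I slope is falsely significant in about 3% of trials. Under pure secular growth with no intervention effect (Phase I mean 20%, Phase II mean 29%), the common slope is significant in about 36% to 40% of trials, but the Phase I slope in only about 7% to 9%.

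**Step 6: early-window analysis.** Omitting the first 3 of 18 months leaves 1,000 × 15/18 = 833 Phase II subjects. If 28% applies from then on, power is 0.91. If those 3 months run at 20% and are kept in, the Phase II mean is 26.7% and power is 0.82.

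**The case against.** Several points on the other side stand.

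- A reader might infer that early Phase II subjects are untreated. Appendix F does not support that. On its definition the workshop and toolkit are the intervention, both are in place before Phase II enrolment, and slow local adaptation is part of the effect as delivered. Diagnostic data also run to 6 months after the last Phase II enrolment, so early enrollees may be diagnosed once adapted tools exist. This softens the dilution in step 6.
- A reader might infer that this is the plan's only look at time. SAP section 7 gives interval widths for comparing two halves of Phase II, and both documents cite temporal drift as a reason for the 1:2 ratio. Some SAP methods text is also redacted. What can be said is that this is the only readable time analysis with a model and a reading rule. The two-halves comparison has no rule and power of only 0.16, 0.40 and 0.32 for uptake over 6, 12 and 18 months. It cannot separate uptake from drift either.
- A reader might infer that a true effect would be reported as an artefact. Section 8.2.1 sets out to examine a possibility, and nothing in it overrides the chi-square, Fisher or Poisson results.
- A much higher trigger rate, about 75%, arises if the Phase II mean is held at 28% with uptake over 18 months. The final rate must then reach 20% + 2 × 8 = 36%, twice the planned increase.
- Relying on the Phase I slope alone would create the opposite error. By step 5 it would miss most real secular growth and credit that growth to the intervention.

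**Conclusion.** The point holds as a defect in a stated model and its reading rule. With uptake over 6 to 18 months to the planned 28%, the step ratio falls from about 1.05 to 0.86 while the true average ratio is 1.33 to 1.20. The confounding label is triggered in about 14% to 30% of trials, a minority. The bias in β2 does not depend on that trigger. At 3 months' uptake the effect is modest (1.20 against 1.37, label in 5%).

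The size rests on an assumed lag, linear uptake, no secular trend, the planned 500 and 1,000 subjects, and mostly a 6-month gap. The same structure applies to the IPG model, for which no size was computed. The documents do not support treating the primary comparisons as invalid, and no model in this uncontrolled sequence can fully separate uptake from drift. The change is worth making because it is cheap and the present rule can give a wrong answer.

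**What to change.** 1. In SAP 8.2.1, add log(Y) = β0 + β1X + β2D + β3D × (X − start of Phase II) + log(Z) for both endpoints, and report it beside the existing model. Replace the reading rule as follows. A trend already visible in Phase I supports temporal confounding. A significant common slope driven by Phase II is reported as unable to separate gradual uptake from secular drift; it is neither called confounding nor credited to the intervention.
2. As a supporting analysis only, repeat both primary comparisons without Phase II subjects enrolled in a pre-specified early window, for example the first 3 months at each centre, or before the centre's tool-use date where one is available. The all-enrolled primary analysis stays, in line with Appendix F.

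**Cost.** One model term, a reworded rule and one supporting analysis. The Phase I slope has little power against real secular change, so both models must be shown. The supporting analysis uses fewer subjects (833 of 1,000 with a 3-month window), and the choice of window is a convention. SAP section 6 says South Asia has already entered Phase II, so tool-use dates may have to be collected retrospectively. The window should be fixed before Phase II outcomes are examined.

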4.4 Minimization of Bias

Potential sources of bias in this study may result from the Hawthorne effect, selection of study centers, selection of subjects, treatment of subjects, and evaluation of study data. The following methods have been incorporated into the study to minimize potential bias.

- Center selection criteria, documented under separate cover, will need to be met prior to participation in IMPROVE Brady
- Study center characteristics will be collected at activation on possible differences that may effect the primary endpoints
- Centers will be used as their own control
- Subjects will be screened to confirm eligibility for enrollment with defined inclusion/exclusion criteria prior to enrollment
- Subject demographics will be collected at baseline on possible differences that may effect the primary endpoints
- It is anticipated that the distribution of subjects with various co-morbidities will vary by study centers. To minimize potential bias, all sites will be encouraged to enroll at least 10 subjects in each study Phase and enrollment at a site cannot exceed 20% of the sample size for the geography/country to ensure a more even distribution of data
- All study Clinicians will be required to follow the Clinical Investigation Plan
- All study clinicians and Medtronic personnel will be trained on their respective aspects of the clinical investigation plan using standardized training materials.

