8.3. Demographic and Other Baseline Characteristics

8.3.1. Description of Baseline Variables

A number of characteristics will be reported for each enrolled subject on baseline case report forms (CRFs) at time of enrollment. The variables collected will include demographics, medical history, symptoms, vitals, and cardiovascular medications. Tables and descriptive statistics will be used to summarize subject data with respect to these variables. For quantitative variables such as age, the mean, standard deviation, median, the first quartile and third quartile, minimum and maximum will be presented. For qualitative variables, counts and percentages will be given.

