8.5.1.1. Analysis Methods

A. Statistical Methodology

To compare the proportion of subjects with an SND diagnosis pre-intervention (Phase I) to the proportion post-intervention (Phase II), a chi-square test will determine statistical significance. The proportion of subjects diagnosed will be evaluated at multiple time points because the time to diagnosis is expected to vary by geography. Thus, times are pre-specified starting at 6 months and any additional 6-month interval thereafter for which there is sufficient follow-up data available to compare study phases.

Proportions calculated at all available time points will be reported. Additionally a Poisson regression will compare the average number of subjects with an SND diagnosis in Phase I and Phase II where the subject time in study is treated as an offset in the model. The above described tests will be performed only for subjects in the South Asia geographical region as per section 6.

[REDACTED]

[REDACTED]

This document is electronically controlled. Printed copies are considered uncontrolled.

Confidential

[REDACTED]

[REDACTED]

[REDACTED]

B. Determination of Patients/Data for Analysis

All subjects that are enrolled in the study will be included in the determination of the proportion estimates. The proportion estimates will be calculated based on information from fixed time points at 6 months of follow-up, 12 months of follow-up, and any additional 6-month interval thereafter for which there is sufficient follow-up data available to compare study phases. The number of subjects that obtain an SND diagnosis by pre-specified time point $t = 6, 12, \text{ etc.}$, is included in the numerator and the number of subjects enrolled is included in the denominator.

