8.5.2.1. Analysis Methods

A. Statistical Methodology

To compare the proportion of subjects that receive indicated therapy pre-intervention (Phase I) to the proportion post-intervention (Phase II), a Fisher's Exact test will determine statistical significance. A Fisher's exact test is recommended for smaller sample sizes. The proportion of subjects diagnosed will be evaluated at multiple time points because the time from diagnosis to implant is expected to vary by geography. Shorter time intervals will be used to evaluate the proportion of implants than for the proportion of diagnosis because time from diagnosis to implant is typically shorter than the time from enrollment to SND diagnosis. Thus, times are pre-specified starting at 3 months and any additional 3-month interval thereafter for which there is sufficient follow-up data available to compare study phases. Proportions calculated at all available time points will be reported. Additionally, a Poisson regression will compare the average number of subjects with an implant where the subject time in study beginning at the time of SND diagnosis is treated as an offset in the model. The above described tests will be performed only for the South Asia geography as described in Section 6. Further, similar tests will compare the differences in the types of therapy received in Phase I and Phase II. For example, a Fisher's exact test will compare the frequency of dual chamber device use pre- and post-intervention.

This document is electronically controlled. Printed copies are considered uncontrolled.

Confidential

B. Determination of Patients/Data for Analysis

Subjects that meet inclusion criteria and obtain an SND diagnosis shall be included in this analysis. The proportion estimates will be calculated based on information from fixed time points at 3 months of follow-up, 6 months of follow-up, and any additional 3-month interval thereafter for which there is sufficient follow-up data available to compare study phases. The number of subjects that obtain an IPG by pre-specified time point $t = 3, 6, \text{ etc.}$, will be included in the numerator and the number of subjects with an SND diagnosis will be included in the denominator.

C. Additional Analyses

- In addition to the overall diagnosis and treatment rates between Phase I and Phase II, various descriptive summaries of the subjects will be explored by geography, including the following:

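### In the readable text, neither primary phase comparison adjusts for subject baseline characteristics or site, so a change in case mix at the phase boundary could not be told apart from the intervention

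*Protocol*

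**What the plan says.** - **Purpose of the baseline data.** Protocol 4.4 names selection of subjects as a possible source of bias. Among the countermeasures it lists "Subject demographics will be collected at baseline on possible differences that may effect the primary endpoints". It adds: "It is anticipated that the distribution of subjects with various co-morbidities will vary by study centers".
- **Planned use of the baseline data.** SAP 8.3.1 states: "The variables collected will include demographics, medical history, symptoms, vitals, and cardiovascular medications". The use it describes is tabulation and descriptive summary.
- **Primary Objective 1.** SAP 8.5.1.1 says "a chi-square test will determine statistical significance". It adds a Poisson regression comparing the phases, "where the subject time in study is treated as an offset in the model".
- **Primary Objective 2.** SAP 8.5.2.1 says "a Fisher's Exact test will determine statistical significance". It adds a Poisson regression with follow-up counted from diagnosis.
- **Confounding.** SAP 8.2.1 begins its reasoning with "Since the study design does not randomize the treatment and control subjects". It plans an interrupted time series rate model for diagnosis and for implant, with calendar time, a phase indicator and a follow-up offset. A significant time coefficient is taken as evidence of temporal confounding.
- **Covariate models.** Patient-level covariates are named only for the secondary time-to-event objectives: an optional Cox model in SAP 8.5.4.1 and a Cox model in SAP 8.5.5.1. Stratification by site appears in Protocol 11.2 for the secondary log-rank tests only.
- **Population.** SAP 6 restricts phase comparisons to South Asia. The geography covariate that SAP 5 planned for overall testing therefore no longer has a role in them.

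**The concern.** Collecting a variable does not control bias unless an analysis uses it. The plan treats baseline characteristics as possible influences on the primary endpoints, and in SAP 8.5.4.1 treats age and gender as possible influences on SND diagnosis. Yet the readable primary comparisons condition on neither these nor site.

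The design leaves room for the mix to change. The phases are sequential. Under Protocol 4.3 the investigators attend a workshop on SND between the phases and are then authorised to enrol Phase II. Protocol 4.2 admits a subject on a sinus or junctional rate of 50 or below, or on a history of exercise intolerance. Protocol 5.3 allows enrolment at any point at which the criteria are met. The Objective 1 denominator is everyone enrolled, so a change in who is enrolled changes the proportion diagnosed even if practice does not change. The error can run either way: a richer mix in Phase II imitates an effect, and a poorer one hides it.

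**Working it through.** **1. The plan's own figure.** SAP 8.5.1.2 gives 500 and 1,000 subjects, 20% against 28%, type I error 0.05 (two-sided assumed) and power 0.90.

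Power = Φ((d − 1.96·s0)/s1), where s0 is the pooled standard error and s1 the unpooled one. Here d = 0.08, the pooled proportion is (100 + 280)/1,500 = 0.253, s0 = 0.0238 and s1 = 0.0228. Power is 0.928, or 0.918 with continuity correction. The difference detectable at 90% power is 7.6 to 7.7 points. The stated 8 points reproduces, but its reading as an intervention effect presumes the same case mix in both phases.

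**2. Effect of a mix shift with no intervention effect.** The documents give no stratum rates, so these are assumptions. A baseline feature has 30% prevalence in Phase I and an SND rate of 35%. To give 20% overall, the rate without it must be (0.20 − 0.30×0.35)/0.70 = 0.136. With Phase II prevalence q, the Phase II proportion is p2 = 0.35q + 0.136(1 − q). The rejection rate uses the formula in step 1; the second figure uses the unpooled error throughout, Φ(d/s1 − 1.96).

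| q in Phase II | p2 | Crude rejection, pooled / unpooled |
|---|---|---|
| 30% | 20.0% | 5% / 5% |
| 40% | 22.1% | 16% / 16% |
| 45% | 23.2% | 29% / 30% |
| 50% | 24.3% | 46% / 48% |

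**3. Range over other assumed strata.** Phase I is split 50:50 between a higher-yield and a lower-yield stratum, again with no intervention effect.

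| Stratum rates | Shift in share | p2 | Crude rejection |
|---|---|---|---|
| 30% / 10% | 10, 20, 30 points | 22%, 24%, 26% | 14%, 41%, 73% |
| 35% / 5% | 10, 20, 30 points | 23%, 26%, 29% | 26%, 73%, 97% |

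A Mantel-Haenszel test stratified on the factor rejects in about 5% of simulated studies in every row.

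**4. Cost in power, and the opposite direction.** With a true effect equivalent to 20% against 28% at constant mix, the stratified test has power of 0.94 to 0.97. An adverse shift of 10 or 20 points cuts crude power to 0.65 or 0.24 (30%/10% strata), or to 0.42 or 0.03 (35%/5% strata).

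**5. Does the SAP 8.2.1 model catch it?** It was simulated (400 runs) with 35%/5% strata, a step in mix at the phase change and no intervention effect. A 20-point step gave a phase rate ratio of about 1.31, and a 30-point step about 1.44. The time coefficient was significant in about 2% and 1% of runs, so the planned check would rarely flag the problem. The phase coefficient was significant in 14% and 28% of runs. That is less often than the crude test, but the estimate carries the bias.

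**6. Room for adjustment in Objective 2.** SAP 8.5.2.2 expects 100 and 200 SND subjects. At 10% in both phases there are 10 + 20 = 30 implants; at 10% against 26% there are 10 + 52 = 62. Phase, age, sex, rate criterion, syncope and nine contrasts for about ten sites make 14 parameters, or 30/14 ≈ 2 to 62/14 ≈ 4 events each. A full model is not supportable there.

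**The case against.** The plan is not silent on confounding. SAP 8.2.1 recognises it and models it for both primary rates. Protocol 11 and SAP 8.4 say that Phase II is doubled partly so that drift in outcomes or subject demographics can be examined, and the baseline tables would show a large shift. Protocol 4.4 uses centres as their own control, encourages ten subjects per phase and caps enrolment per site. SAP 6 limits by-site analyses to sites enrolling in both phases. SAP 4.1 calls the primary objectives exploratory.

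Much of this stands, and it rules out a stronger reading that a reader might be tempted by: that the plan ignores confounding, or that no primary analysis anywhere uses baseline data. The documents do not support that. Besides SAP 8.2.1, part of SAP 8.5.1.1 is redacted directly after the Poisson description, so one can say only that the readable text names no covariate.

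The narrower gap remains. The time-series model contains no subject covariates. No method is given for acting on demographic drift once it is seen. The site rules limit imbalance between centres, but the pooled tests do not condition on site. Exploratory status softens the inference, yet significance tests and power are still specified.

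**Conclusion.** The point holds in this limited form: the readable primary phase comparisons adjust for neither subject baseline characteristics nor site, and the SAP 8.2.1 model covers linear calendar drift rather than a step in case mix at the phase boundary.

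For Objective 1, under the 35%/13.6% strata, a shift of 10 to 20 points produces 2.1 to 4.3 points of spurious increase and a crude rejection rate of about 16–48% instead of 5%. The largest of these is about half the planned 8-point effect. The more strongly separated strata in step 3 give larger figures. All of these rest on assumed stratum rates and shifts; none comes from the documents. No size has been computed for Objective 2.

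A reader might infer that case mix did shift and that the primary result will be wrong. Nothing in the documents shows that, and the same entry criteria apply in both phases. The defect is conditional: if the mix shifted, the primary analysis as described could not separate the shift from the intervention. This is an inexpensive improvement worth making, not a flaw that invalidates the design.

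**What to change.** - **SAP 8.5.1.1 (Objective 1).** Pre-specify an adjusted version of the planned Poisson regression with robust variance. Terms: phase, age, sex, whether the criterion of a sinus or junctional rate of 50 or below was met (yes/no), syncope at baseline, and site as strata or a clustering term. The rate criterion should be coded yes/no because Protocol 4.2 requires at least one heart-rate criterion, so a subject may meet both. Site strata remove differences in centre mix; cluster-robust variance alone corrects only the standard error. Report the adjusted phase rate ratio with its 95% CI beside the crude test.
- **SAP 8.2.1.** Add the same covariates to the time-series model for diagnosis.
- **SAP 8.5.2.1 (Objective 2).** Add a sensitivity analysis limited to two or three terms, for example age and sex, with site handled by stratification or clustering. Apply the same limit to the implant version of the SAP 8.2.1 model.

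The cost is SAP wording, a few model terms and a little analysis time. Demographics, symptoms, vital signs and eligibility are already baseline items in Protocol 5.2, so no new data collection should be needed. In the scenarios checked, stratifying cost no power.

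Two limits should be stated in the SAP. Adjustment handles measured factors only. Symptoms or entry route recorded in Phase II may themselves be influenced by the training, so the adjusted result should be read beside the crude one rather than in place of it.
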